# 3.2 Exclusion Criteria

### Subjects who meet *any* of these criteria are *not* eligible for participation in the study:

- 1. Known IgE mediated allergy to antibiotics and antifungal medications (ciprofloxacin, gentamycin, and amfotericin B) used in the culture medium.
- 2. Known hypersensitivity to dextran.
- 3. Body mass index (BMI) >30 kg/ $m^2$
- 4. Insulin requirement of > 1.0 IU/kg/day
- 5. HbA1c >10%.
- 6. Untreated proliferative diabetic retinopathy.
- 7. Blood Pressure SBP >160mmHg or DBP > 100mmHg.

[figure not shown]
- Measured glomerular filtration rate (GFR) using 51Cr-EDTA, 99technetium-DPTA, or iohexol <80 ml/min/1.73 m^2. The absolute (raw) GFR value will be used for subjects with body surface areas >1.73 m^2.
- 9. Presence or history of macroalbuminuria (>300mg/g creatinine).
- 10. Presence or history of panel-reactive anti-HLA antibodies >80% by flow cytometry. Subjects with panel reactive anti-HLA antibodies above background but ≤ 80%, can be included if the antigen specificity of the antibodies can be determined for future avoidance; however, if the antigen specificity of the antibodies cannot be determined they will be excluded
- 11. For female subjects: Positive pregnancy test, presently breast-feeding, or unwillingness to use effective contraceptive measures for the duration of the study and 4 months after discontinuation. For male subjects: intent to procreate during the duration of the study or within 4 months after discontinuation or unwillingness to use effective measures of contraception. Oral contraceptives, Norplant®, Depo-Provera®, and barrier devices with spermicide are acceptable contraceptive methods; condoms used alone are not acceptable.
- 12. Active infection including hepatitis B, hepatitis C, or HIV.
- 13. Negative screen for Epstein Barr Virus (EBV) by IgG determination.
- 14. Any history of malignancy except for completely resected squamous or basal cell carcinoma of the skin.
- 15. Known active alcohol or substance abuse.
- 16. Baseline Hgb below the lower limits of normal at the local laboratory; lymphopenia (<1,000/μL), neutropenia (<1,500/μL), or thrombocytopenia (platelets <100,000/μL).
- 17. Homocygotic Activated Protein C Resistance (APC-R).
- 18. History of hypercoagulability disorder or coagulopathy or international normalization ratio (INR) >1.5.
- 19. Known history of severe co-existing cardiac disease, characterized by any one of the following conditions:
  - a. Recent myocardial infarction (within past 6 months).
  - b. Evidence of ischemia on functional cardiac exam within the last year.
  - c. Left ventricular ejection fraction <30%.
- 20. Consistently abnormal liver function tests at the time of study entry. SGOT (AST), SGPT (ALT), Alk Phos or total bilirubin, with values >1.5 times normal upper limits on two consecutive measurements > 2 weeks apart.
- 21. Acute or chronic pancreatitis.
- 22. Patients with active peptic ulcer disease, symptomatic gallstones, or a history of portal hypertension.
- 23. Severe unremitting diarrhea, vomiting or other gastrointestinal disorders potentially interfering with the ability to absorb oral medications.
- 24. Receiving treatment for a medical condition requiring chronic use of systemic steroids, except for the use of <5mg prednisone daily, or an equivalent dose of hydrocortisone, only for physiological replacement.
- 25. Treatment with any-anti-diabetic medication, other than insulin, within 4 weeks of enrollment.
- 26. Use of any investigational agents within 4 weeks of enrollment.
- 27. Administration of live attenuated vaccine(s) within 2 months of enrollment.
- 28. Patients with any condition or any circumstance that in the opinion of the investigator would make it unsafe to undergo an islet transplant.
- 29. Treatment with any immunosuppressive regimen at the time of enrollment.
- 30. A previous islet transplant.
- 31. A previous pancreas transplant, unless the graft failed within the first week due to thrombosis, followed by pancreatectomy and the transplant occurred more than 6 months prior to enrollment.

### 4. STUDY DESIGN

This is an open label, stratified, randomized, multi- center study that will be conducted in 7 centers in Scandinavia (Norway, Sweden, Finland, and Denmark).

#### **Enrollment**

- 1. Obtain informed consent from potential subject.
- 2. Enroll eligible subjects using the Internet system and receive computer generated unique subject ID #.

• If a third islet transplant occurs less than 75 days after the second transplant, then the 75 day endpoint data for the second transplant will not be performed.

Subjects who are more than 8 months past the first islet transplant, are no longer eligible for additional islet transplants under this protocol.

#### Figure 4: Study Design Schema: Enrollment, Screening, Randomization, and Transplantation

#### **4.1 Study Endpoints** 4.1.1 Primary Endpoint

The level of stimulated c-peptide at 90-minutes derived from the mixed-meal tolerance test (MMTT) at 75+5 days following the first islet infusion.

### 4.1.2 Secondary Endpoints

The target level for HbA1c chosen for this study is 7.0%. This value was chosen because it is the level recommended by the American Diabetes Association (ADA) and is considered to be the clinically relevant goal for subjects with T1D. A HbA1c level of 6.5% is the goal recommended by the American College of Endocrinology (ACE).

A severe hypoglycemic event is defined as an event with one of the following symptoms: memory loss; confusion; uncontrollable behavior; irrational behavior; unusual difficulty in awakening; suspected seizure; seizure; loss of consciousness; or visual symptoms, in which the subject was unable to treat him/herself and which was associated with either a blood glucose level < 54 mg/dL [3.0 mmol/L] or prompt recovery after oral carbohydrate, IV glucose, or glucagon administration.

- 1. TAT complexes and C-peptide immediately prior to islet infusion, when 125 mL is left in the infusion bag (before rinsing) at 0, 15, 60, 180, 270 and 360 minutes after completion of the islet transplant, and 24 hours after completion of islet transplant;
- 2. Conduction Velocity and RR interval at screening, and month 12 after first and last islet transplant;
- 3. Portal pressure before and 15 minutes after completion of islet transplantation;
- 4. Liver enzymes (ALT, AST), one and seven days after all islet transplantation(s);
- 5. Quality of life (DTSQs, DTSQc, SF36 Questionnaires), 1 year after the first and final islet infusion, to be compared with the same test done as a part of the screening prior to being put on the waiting list (DTSQs);
- 6. Percentage of administered radioactivity found in the liver after the start of islet transplantation. Determined through the use of PET/CT (protocol section 9.1.1.11).

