	The protocol includes the following induction drugs; Rabbit anti-thymocyte globulin (ATG, Thymoglobulin®) for the initial islet transplant, for a second or third transplantation a_monoclonal IL-2 receptor blocker, Basiliximab (Simulect
	$^{\textcircled{B}}$ ), replaces Rabbit anti-thymocyte globulin. In addition, the protocol contains one cell proliferation inhibitor
	(CellCept ® or Rapamune ® ) and one calcineurin inhibitor (Prograf ® or Sandimmune Neoral ® ). The protocol includes one Anti-Inflammatory agent, Etanercept (Enbrel ® ).
Primary Endpoint	The level of stimulated c-peptide at 90-minutes derived from the mixed-meal tolerance test (MMTT) at 75 + 5 days following the first islet infusion.
Secondary Endpoints	
 
TAT complexes and C-peptide immediately prior to islet infusion, when 125 mL is left in infusion bag (before rinsing), and at 0, 15, 60, 180, 270, 360 minutes after completion of islet transplant, and 24h after completion of islet transplant;
 
Conduction Velocity and RR interval at screening, and month 12 after first and last islet transplant;
 
Portal pressure before and 15 minutes after completion of islet transplantation;
 
Liver enzymes (ALT, AST), one and seven days after all islet transplantation(s);
 
Quality of life Questionnaires (DTSQc, SF36), 1 year after the first and last islet transplantation, to be compared
 

with the same test done as a part of the screening prior to being put on the waiting list (DTSQs).6. Percentage of administered radioactivity found in liver after the start of islet transplantation. Determined through the use of PET/CT (protocol section 9.1.1.1)

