## 7.2 Waiting List / Baseline Visit

During the period when the subject is awaiting for their first transplant, they will return to the study site for clinic visits every 6 months. Waitlist assessments will be repeated at pre-defined intervals as detailed below. Results from assessments done closest to the date of randomization will be used as the subject's baseline values.

Waitlist Assessments	Timetable for repeat testing while on the waiting list
Retinopathy Evaluation; Physical Exam; Chest x-ray; ECG; Coagulation Status (APTT, PK, fibrinogen, platelets); CGMS; Serology (HIV, Hepatitis B, Hepatitis C	Once a Year
CBC with differential; Serum Chemistry Panel; Glycemic Lability- LI ( repeat only if used as inclusion criteria); Glycemic Lability (MAGE); Alloantibodies; Quality of Life Questionnaires (SF36, DTSQ); HbA1C; Blood Sugar Records and Hypo sheets; Full Hypo Score; Clarke Score.	Once every 6 months
Baseline Assessments	
Re-evaluation of the eligibility criteria; Record concomitant medications; CMV and EBV by PCR; Autoantibodies; RNA and Plasma to Archive; Alloantibodies; Physical Exam; CBC with differential; Serum Chemistry Panel; Coagulation Status (APTT, PK, fibrinogen, platelets); Blood Sugar Records and/or Hypo sheets; Serology (HIV, Hepatitis B, Hepatitis C); Chest x-ray; ECG; Cross Match; Serum Pregnancy Test; HbA1C	At the time the pancreas becomes available, prior to transplant

Table 3. Baseline/Waiting List Assessment Windows

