## **APPENDIX 1: SCHEDULE OF EVENTS**

							DAY					MC	NTH	1 Yr post 1 st Tx 
Time points	Screen	WL	BL	Transplant	1	3	7	14	21	28	75 	6	12	
Visit Number	01		02	03	04	05	06	07	08	09	10	11	12	Y1
Visit Windows (Days)	N/A			±0	±0	±0	±3	±3	±3	±3	±5	±14	±14	±14
(2 4 5 5)			CEN	JERAL ASSES										
Informed consent	X		ULI											
Evaluation of Eligibility Criteria	X		X											
Quality of Life (SF36, DTSQ) 	X	Х									X 1		X	Х
Medical and Diabetes History	X													-
Retinopathy Evaluation	X	Х												Х
Physical Exam and Vital Signs (Weight, Height  , BMI  , Temperature,	x	x	x	x	x	x	x	x	x	x	x	x	x	x
Pulse, Blood Pressure)	X	Х	X											
Chest X-Ray	X	Λ	Λ	X	X									
Abdominal Ultrasound	-			^	Λ									
ECG, Myocardial Scintigram	Х	X4	X4											
Conduction Velocity and RR intervals	Х												Х	Х
Immunosuppression Medications				$\rightarrow$	$\rightarrow$	$\rightarrow$	$\rightarrow$	$\rightarrow$	$\rightarrow$	$\rightarrow$	$\rightarrow$	$\rightarrow$	$\rightarrow$	$\rightarrow$
Concomitant Medications			$\rightarrow$	$\rightarrow$	$\rightarrow$	$\rightarrow$	$\rightarrow$	$\rightarrow$	$\rightarrow$	$\rightarrow$	$\rightarrow$	$\rightarrow$	$\rightarrow$	$\rightarrow$
Assessment of AE, SAE, Infections, Hospitalizations, Rejections	$\rightarrow$	$\rightarrow$	$\rightarrow$	$\rightarrow$	$\rightarrow$	$\rightarrow$	$\rightarrow$	$\rightarrow$	$\rightarrow$	$\rightarrow$	$\rightarrow$	$\rightarrow$	$\rightarrow$	$\rightarrow$
Blood Sugar Record eCRF	X5	X5	X5								X5	Χ5	X5	X5
Glucometer Download	X5	Χ5	X5	X5			Х	Х	X	Х	X5	X5	X5	X5
Insulin Requirement (Total U/24 h) 	X 	X 	X 	X 			X	X	X	X	X 	X 	X 	X 
Portal Pressure				X 6										
	•	LOC	CAL LA	BORATORY	ASSES	SMEN	NTS	•						
HLA, Blood Type	Х													
Cross Match			Х											
CBC with differential 	Х	Х	Х	X 7	X 7	X 7	Х	X 7	X 7	Х	Х	Х	Х	Х
Serum chemistry panel  and CRP	x	Х	Х	X	Х	Х	Х	Х	Х	Х	Х	Х	х	Х
Coagulation Status (APTT, PK, fibrinogen, platelets)	х	Х9	x	Х9	x	x	x	x	x	x	х		х	x
Urine Albumin	Х										Х		Х	Х
Fasting Lipid Profile (Total, LDL, HDL, Triglycerides)	х			х						x	x	x	х	х
Glomerular Filtration Rate (GFR)	Х										X 10		Х	Х
Serum Pregnancy Test	Х		X11											-
Fast. & Postprandial Plasma Glucose						X	X	X	X	X12				-

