17 Results based on the HbA1c, Insulin requirement, and fasting (basal) serum glucose and stimulated C-peptide from the MMTT (Ryan, et al)

18 Results based on the fasting (basal) serum glucose and c-peptide from the MMTT and the simultaneous serum creatinine.

19 This is a substudy to be completed in a subset of subjects (n=8, 4 LMW-DS, 4 Control) at selected sites.

20 Central Laboratory assessment: U. Pennsylvania (Philadelphia, PA)

21 Central laboratory assessment: The Barbara Davis Center Laboratory (Denver, CO)

22 Central laboratory assessment: The Rudbeck laboratory (Uppsala, Sweden)

23 Central Laboratory: The NIDDK Repository

24 Only SF36 completed during the baseline / wait list visits. DTSQs completed during the screening visit and DTSQc completed at the 12 month post first and final islet transplant.

25. Repeat the LI or HYPO during the Baseline/Waitlist period only if the inclusion criteria for study enrollment (inclusion criteria #7b or #7c) were used for inclusion in the study.

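### The protocol contradicts itself on which DTSQ version is given when; under schedule footnote 24 no DTSQ version is common to screening and one year, so the stated DTSQ comparison with screening cannot be made

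*Protocol*

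**What the plan says.** Five places in the Protocol govern this endpoint.

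- **Section 4.1.2, item 5.** The forms at one year are "Quality of life (DTSQs, DTSQc, SF36 Questionnaires), 1 year after the first and final islet infusion". They are "to be compared with the same test done as a part of the screening prior to being put on the waiting list (DTSQs").
- **Synopsis, Secondary Endpoints, item 5.** The forms at one year are "Quality of life Questionnaires (DTSQc, SF36), 1 year after the first and last islet transplantation, to be compared" with the screening test, which is again named as DTSQs. DTSQs is not listed at one year.
- **Appendix 1, Schedule of Events.** The row reads "Quality of Life (SF36, DTSQ"), with no version given. It is marked at screening, waiting list, day 75, month 12 and the visit one year after the first transplant. Footnote 24 supplies the versions: "DTSQs completed during the screening visit and DTSQc completed at the 12 month post first and final islet transplant". On the waiting list it says "Only SF36 completed during the baseline / wait list visits".
- **Section 7.2, Table 3.** "Quality of Life Questionnaires (SF36, DTSQ") are repeated every 6 months on the waiting list, version not stated.
- **Appendix 2, reduced follow-up.** A quality-of-life questionnaire is due one year after the initial and one year after the last transplant, by mail or in person. The instrument is not named.

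Section 9.1.1.10 names DTSQs and DTSQc separately, so the protocol treats them as two instruments. Section 10.2.2 plans a t-test for quality-of-life scales and gives no formula for change from screening.

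**The concern.** The endpoint is worded as a comparison of one-year results with an identical test taken at screening. That needs at least one DTSQ version given at both times. The Synopsis and footnote 24 place one version at screening and the other at one year, and footnote 24 is what a site would consult when handing out forms.

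This is a question of data collection, not of analysis detail. A statistical analysis plan can choose a score or a test, but it cannot supply a questionnaire that was not given at the visit. If the conflict is left until analysis, the DTSQ comparison with screening may be lost. It may also exist only for subjects whose site followed 4.1.2 instead of the footnote.

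**Working it through.** There is no figure to reproduce: the protocol states no effect size or power for this endpoint. The check is to set out which form each text assigns to each time.

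| Text | Screening | Waiting list / baseline | Day 75 | One year (first and final) |
|---|---|---|---|---|
| 4.1.2, item 5 | DTSQs named as comparator | not stated | not stated | DTSQs, DTSQc, SF36 |
| Synopsis, item 5 | DTSQs named as comparator | not stated | not stated | DTSQc, SF36 |
| 7.2, Table 3 | – | SF36, DTSQ (version open), every 6 months | – | – |
| Appendix 1 row | SF36, DTSQ (version open) | SF36, DTSQ (version open) | SF36, DTSQ (version open) | SF36, DTSQ (version open) |
| Appendix 1 footnote 24 | DTSQs | SF36 only | silent | DTSQc |
| Appendix 2 | – | – | – | instrument not named |

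**Step 1: forms available at both times under the schedule as footnote 24 qualifies it.** Screening has DTSQs and SF36. One year has DTSQc and SF36. The only common form is SF36. By schedule, then, 0 of the 36 planned subjects would have the same DTSQ version at screening and at one year, whether the year is counted from the first or the final infusion. The Synopsis gives the same result.

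**Step 2: the same check under 4.1.2 taken literally.** Screening has DTSQs and, from the schedule row, SF36. One year has DTSQs, DTSQc and SF36. The common forms are DTSQs and SF36, so the stated DTSQ comparison is available. Whether the endpoint can be evaluated as worded therefore depends on which text the site follows.

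**Step 3: the Synopsis on its own terms.** It gives DTSQc at one year, calls for comparison with an identical screening test, and names that test as DTSQs. For the DTSQ part, this sentence contradicts itself without reference to any other section.

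**Step 4: the other visits.**
- On the waiting list, Table 3 and the schedule mark call for DTSQ, while footnote 24 limits those visits to SF36.
- At day 75, the row is marked and footnote 1 drops the quality-of-life surveys only after a second or third transplant. A DTSQ form is therefore due after the first transplant, but no version is named.
- Section 7.2 takes the results nearest randomization as baseline, whereas 4.1.2 fixes the comparator for this endpoint at screening. A DTSQ repeated on the waiting list would leave open which value applies.

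**The case against.** The strongest reply is that nothing has been shown to be impossible. Section 4.1.2 itself lists DTSQs at one year, and a site that follows the endpoint text will collect the pair. Footnote 24 also need not be exhaustive: its word of restriction applies to SF36 at the waiting-list visits, not to the DTSQ forms, and it is silent on day 75 although the row is marked there. This stands, and it limits the point. The defect is a contradiction between passages, and the loss of the comparison is conditional on footnote 24 or the Synopsis being followed.

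A reader might go further and infer that the plan subtracts screening DTSQs from one-year DTSQc and so yields a meaningless change score. The documents do not support that. They speak of a comparison, section 10.2.2 gives only a t-test, and no subtraction or change score is defined. Nor does the protocol say what each form asks or how it is scored, so no argument here can rest on that.

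A reader might also infer that the whole quality-of-life endpoint fails. It does not. SF36 is scheduled at screening and at one year, and one-year DTSQc can be compared between arms by the planned t-test.

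What the reply does not remove is that the only text assigning versions to visits disagrees with the endpoint definition, and that a between-arm comparison of DTSQc is not the comparison with screening that both statements of the endpoint name.

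**Conclusion.** The inconsistency is real and should be corrected. Section 4.1.2, the Synopsis, Table 3 and footnote 24 do not agree on which DTSQ version is given when. On the assumption that sites follow footnote 24 as a complete instruction, the DTSQ part of secondary endpoint 5 cannot be compared with screening as stated, for any of the planned subjects and at either anniversary. If sites follow 4.1.2 instead, the comparison survives.

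The effect is confined to the DTSQ component of one secondary endpoint. The SF36 component, the primary endpoint, the power calculation and the safety analyses are untouched. It still merits action because forms not given cannot be recovered later and the remedy is small.

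**What to change.** Reconcile the passages before the one-year visits take place.

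1. Amend footnote 24 and the Synopsis so that DTSQs is given alongside DTSQc one year after the first and the final infusion, as 4.1.2 already lists. Name the same forms in the Appendix 2 questionnaire line.
2. State the two DTSQ comparisons separately: one-year DTSQs with screening DTSQs, and one-year DTSQc between arms on its own. Keep screening as the comparator, because 4.1.2 names it.
3. Make Table 3, the schedule row and footnote 24 agree on whether DTSQ is given on the waiting list, and name the version due at day 75.

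If DTSQs is not to be added at one year, define the DTSQ part of the endpoint as one-year DTSQc compared between arms, and remove the reference to an identical screening test for DTSQ in both 4.1.2 and the Synopsis.

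The first route costs one short questionnaire at visits where questionnaires are already completed, plus the wording changes. The alternative costs wording only, but gives up the DTSQ comparison with screening.

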### 4.1.3 Efficacy Endpoints

### At 75 ± 5 days following the first infusion:

- The percent reduction in insulin requirements
- HbA1c
- Mean amplitude of glycemic excursions (MAGE)
- Glycemic lability index (LI)
- Clarke hypoglycemia awareness score
- Ryan hypoglycemia severity (HYPO) score
- Basal (fasting) glucose and c-peptide and 90-min glucose derived from the mixed-meal tolerance test
- β-score
- C-peptide:glucose creatinine ratio
- Acute insulin response to glucose (AIRglu), insulin sensitivity, and disposition index derived from the insulin-modified frequently-sampled intravenous glucose tolerance (FSIGT) test
- Glucose variability and hypoglycemia duration derived from the continuous glucose monitoring system® (CGMS)
- The proportion of subjects with full islet graft function.

### At 365 ± 14 days following the first and final islet infusion:

- The proportion of subjects with full islet graft function
- The proportion of subjects with an HbA1c <7.0% and free of severe hypoglycemic events from day 28 through day 365
- The percent reduction in insulin requirements

- HbA1c
- MAGE
- LI
- Clarke score
- HYPO score
- Basal (fasting) and 90-min glucose and C-peptide (MMTT)
- β-score
- C-peptide:glucose creatinine ratio
- Acute insulin response to glucose (AIRglu), insulin sensitivity, and disposition index derived from the insulin-modified frequently-sampled intravenous glucose tolerance (FSIGT) test
- Glucose variability and hypoglycemia duration derived from the continuous glucose monitoring system® (CGMS)
- The proportion of subjects receiving a second islet infusion
- The proportion of subjects receiving a third islet infusion

### 4.1.3.1 FULL ISLET GRAFT FUNCTION DEFINITION:

Islet transplant recipients are considered to have full islet graft function if all of the following criteria are met:

- Titrated off insulin therapy for at least 1 week (7 consecutive days) with the last day within the day 75 and day 365 windows;
- HbA1c <7.0% or a 2.5%% decreased from baseline at the end of the 7 day period when titrated off insulin;
- Fasting capillary glucose level should not exceed 140 mg/dL (7.8 mmol/L) more than three times in the past week (based on measuring capillary glucose levels a minimum of 7 times in a seven day period);
- 2-hour post-prandial capillary glucose should not exceed 180 mg/dl (10.0 mmol/L) more than three times in the past week (based on measuring capillary glucose levels a minimum of 21 times in a seven day period);
- Fasting serum glucose level ≤ 126 mg/dL (≤7.0 mmol/L) from central lab results; if the fasting serum glucose level is > 126 mg/dL (>7.0 mmol/L), it must be confirmed in an additional one out of two measurements;
- Evidence of endogenous insulin production defined as fasting or stimulated C-peptide levels ≥ 0.5 ng/mL (≥0.16 nmol/L) at the end of the 7 day period when titrated off insulin.

